## VERSION HISTORY

RAP Version	Approval Date	Protocol Version (Date) on which SAP is Based	Change	Rationale
1	21Feb2019	Protocol Amendment 1 (12Dec2018)	Not Applicable	Original Version
2	22Jan2020	Protocol Amendment 1 (12Dec2018)	
Removal of Part 1B, Part 2A and 2B.
 
Further detail provided for study population analyses.
 
Removal of efficacy section.
 
Added pharmacodynamic/ biomarker analysis section.
 
Added in list of data displays.
	To focus on IB and FDA reporting efforts.
3	01Feb2024	Protocol Amendment 7 (04Aug2023)	
CCI [REDACTED]  [REDACTED]  [REDACTED]
 
Updated RAP according to early study closure, including reducing the list of outputs (includes removal of pharmacodynamic/ biomarker analysis section).
 
Dose escalation method changed to BLRM.
 
Updated study design and analysis sets.
 
Added in crossover considerations.
 
Added in efficacy section.
	
CCI [REDACTED]  [REDACTED]  [REDACTED]
 
Protocol amendments since previous RAP version.
 
Introduction of RAPIDO DV to reduce the number of static listings to be produced.

			
Updated RAP text and list of outputs to remove those that will be produced by RAPIDO DV.
 
Updated the outputs required for the IB based on the streamlining of the IB (data cut off in 2023).
 
General corrections and minor updates.
	
4	See Veeva	Protocol Amendment 7 (04Aug2023)	
Clarification added to the secondary endpoint.
 
Confirmation that the study will transition to PACT (Section 3.3).
 
General corrections, clarifications, and minor updates.
	Final review prior to database lock.

The RAP versions can be found under the following files and versions in Veeva (due to the migration of the documents into Veeva during the study).

RAP Version	Approval Date	Veeva File Name	Veeva Version(s)
1	21Feb2019	Statistical Analysis Plan RAP Critical Components	1-5
2	22Jan2020	Statistical Analysis Plan RAP-Reporting and Analysis Plan for IB and FDA outputs	1-3
3	01Feb2024	Statistical Analysis Plan RAP-Reporting and Analysis Plan for IB and FDA outputs	4
4	See Veeva	Statistical Analysis Plan RAP-Reporting and Analysis Plan for IB and FDA outputs	5

## 1. INTRODUCTION

The purpose of this reporting and analysis plan (RAP) is to describe the analyses to be included in the Clinical Study Report (CSR) for Protocol:

Protocol Revision Chronology:		
2017N347464_00	12-SEP-2018	Original Protocol
2017N347464_01	12-DEC-2018	Protocol Amendment 1
2017N347464_02	27-AUG-2020	Protocol Amendment 2
2017N347464_03	16-OCT-2020	Protocol Amendment 3
TMF-11921930	21-APR-2021	Protocol Amendment 4
TMF-14427782	19-JAN-2022	Protocol Amendment 6
TMF-16209529	04-AUG-2023	Protocol Amendment 7

CCI

[REDACTED]

[REDACTED]

[REDACTED]. A synoptic CSR will be used to report the study and the RAP reflects the reduced list of outputs required for a synoptic CSR (and disclosure).

The RAP focuses on the outputs required for the final analysis, which will be included in the CSR. The RAP also covers two other types of reporting efforts: Dose Escalation Meetings (DEMs) and Investigator Brochure (IB) updates. Note that Statistics and Programming (S&P) provided the outputs for the monotherapy DEMs (Part 1A) and the Study Team provided outputs for the combination DEMs (Part 2A) using appropriate in-stream software. Outputs for the DEM and IB update reporting efforts, which are not required for the final analysis, are included in the RAP but are distinguished from those needed for the final analysis.

This study will utilize the system RAPIDO DV for the final analysis to aid with data visualization. Therefore, only listings that will be produced statically will be discussed in the RAP and included in the list of data displays in the Appendix. Where listings were produced statically for DEMs and IB updates, these will continue to be included in the RAP and will be distinguished as such.

### 1.1. Imaging Substudy

The analyses for the primary and secondary endpoints for the Imaging Substudy are detailed in a separate plan produced by the Amsterdam University Medical Centers (AUMC). CCI

[REDACTED]

[REDACTED]

[REDACTED].

In summary, all applicable analyses for the Imaging Substudy are detailed in separate analysis plans, when performed. Therefore, the Imaging Substudy will not be discussed

**CONFIDENTIAL**

in this RAP. Note that the participants in the Imaging Substudy will still be included in the analyses for the main study endpoints.

## 2. SUMMARY OF KEY PROTOCOL INFORMATION

### 2.1. Changes to the Protocol Defined Statistical Analysis Plan

There were no changes or deviations to the originally planned statistical analysis specified in the current protocol (Protocol Amendment 7, dated 04 Aug 2023). However, due to the early closure of the study, some analyses or displays described in the protocol may no longer be required. Clarification has been given in the RAP on the secondary endpoint regarding PK parameters.

[figure not shown]
### 2.2. Study Objective(s) and Endpoint(s)

Dose Escalation (Part 1A GSK3745417 Monotherapy and Part 2A Combination GSK3745417 and Dostarlimab)	
Objectives	Endpoints
Primary Objectives	Primary Endpoints

 
To determine the safety, tolerability, and the recommended phase 2 dose (RP2D) of GSK3745417 alone or in combination with dostarlimab administered intravenously to participants with advanced/recurrent solid tumors.
 
	
 
Incidence of DLT.
 
Incidence and severity of adverse events.
 

Secondary Objectives	Secondary Endpoints

 
To characterize the PK properties of GSK3745417 alone or in combination with dostarlimab.
 
	
 
GSK3745417 concentrations in plasma and PK parameters including AUC(0-tau), maximum observed concentration (Cmax), and terminal half-life (t1/2), as data permit.
 

Exploratory Objectives	Exploratory Endpoints

CCI

[figure not shown]
**CONFIDENTIAL**

CCI

**CONFIDENTIAL**

CCI

[figure not shown]
## 2.3. Study Design

CCI

Design Features	

• In Part 1A, safety and tolerability of escalating doses of GSK3745417 (Q1W in Arm A1 and Q3W in Arm A2) will be evaluated according to Bayesian Logistic Regression Model (BLRM) design.

○ Part 1A was completed.

• In Japan, a stand-alone monotherapy dose escalation will be conducted to evaluate the safety, tolerability, PK/PD and preliminary clinical activity of GSK3745417(Q1W) in a Japanese population. The safety and tolerability of escalating doses of GSK3745417 (Q1W) will be evaluated, and a 3+3 dose-escalation procedure will be utilized.

○ The Japan monotherapy dose escalation was prematurely stopped.

• Note that upon the clearance for safety of a dose in Part 2A combination therapy dose escalation, participants in Part 1A (including the Japan monotherapy cohorts) may be considered at confirmed disease progression and on a case-to-case basis to transition to a cleared combination dose/frequency regimen as tested in Part 2A.

• Once a dose of GSK3745417 has been identified that is tolerable and demonstrates potential pharmacodynamic activity (based on the totality of the data), enrolment in Part 2A may begin. Starting at a dose of 0.1 mg

-----------------	---

**CONFIDENTIAL**

CCI

Overview of Study Design and Key Features	
	CCI [REDACTED]
Time & Events	
 
• [Refer to Appendix 2: Schedule of Activities]
 

Treatment Assignment	
 
• This is a first time in human, open label, repeat dose, non-randomized study.
 
• BLRM will be used to guide the dose escalation decisions in Parts 1A and 2A.
 
• The 3+3 dose-escalation procedure will be used to guide the dose escalation decisions in the Japan monotherapy cohort.
 
• CCI [REDACTED] [REDACTED]
 

Interim Analysis	
 
• For dose escalation and de-escalation decisions, preliminary safety and available PK/Pharmacodynamic data will be analysed and reviewed by the Study Team (to include at minimum, the GSK medical monitor and investigators) after completion of each dose cohort. This review will support the decision on the dose level in the next dose cohort.
 
• Additional interim analyses may be conducted in any part of the study to support IB/Development Safety Update Reports, publications, internal governance board meetings, and planning of future studies.
 

## 2.4. Statistical Hypotheses / Statistical Analyses

CCI

### 3. PLANNED ANALYSES

#### 3.1. Part 1A and 2A: Dose Escalation (Monotherapy and combination therapy with dostarlimab)

Dose escalation for GSK3745417 monotherapy will begin with a starting dose of 0.1 mg in both Arm A1 and Arm A2. There will be two arms in Part 1A: GSK3745417 monotherapy at every 1-week interval (Q1W) in Arm A1, and GSK3745417 monotherapy at every 3-week interval (Q3W) in Arm A2. The first 3 participants in the first 4 dose levels in each arm will begin treatment  $\geq$ 48 hours apart to allow assessment of initial safety data in each participant before beginning the next participant's treatment. This staggered dosing start is not required for participants enrolling at previously cleared dose levels and may be waived once sufficient data are available. In exceptional cases, intra-participant dose escalation allowing participants to move from a lower to a higher dose not exceeding the MTD will be discussed with investigators and approved by the GSK Medical Monitor. Once a 21-day for Arm A1 or 29-day for Arm A2 DLT evaluation period has been completed, BLRM analysis will be performed to guide the dose level to which the next 3 participants will be assigned based on the posterior probability of the DLT rate.

Select outputs will be provided by S&P for monotherapy dose escalation meetings (Part 1A). These are indicated in Appendix 10 by the DEM reporting effort. The following outputs were created for DEMs only and are therefore not referred to in the main RAP text:

- A summary of the number of DLTs, adverse events (AEs) and serious adverse events (SAEs) for all DLT evaluable subjects
- A summary of the number of events and subject by maximum grade for DLT evaluable subjects
- A listing of serious adverse events for DLT evaluable subjects
- A listing of grade  $\geq 3$  laboratory data for complete blood count (CBC) with differential for DLT evaluable subjects

There will be two arms in Part 2A: combination of GSK3745417 Q1W and dostarlimab in Arm A3, and combination of GSK3745417 Q3W and dostarlimab in Arm A4. Dostarlimab will be added to this regimen starting at Week 1 of the GSK3745417 dosing schedule and administered at 500 mg dose Q3W for the first 4 doses, followed by 1000 mg Q6W for subsequent doses. The first 3 participants in each dose level will begin treatment  $\geq$ 48 hours apart to allow assessment of initial safety data in each participant before beginning the next participant's treatment. Each participant must complete the 29-day DLT evaluation period and the available safety data must be reviewed before a decision is made on whether to proceed to the next dose level. Once a 29-day DLT evaluation period has been completed, BLRM analysis will be performed to guide the dose level to which the next 3 participants will be assigned based on the posterior probability of the DLT rate. If a participant withdraws from the study before completion of the 29-day DLT period for reasons other than DLT, the participant will not be counted as DLT evaluable and will be replaced.

For the combination dose escalation meetings (Part 2A), the outputs for the DEMs will be provided by the Study Team (not S&P) using appropriate, in-stream software.

### **3.1.1. Description of the Bayesian Logistic Regression Model (BLRM)**

After each dose cohort, BLRM will be used to guide dose escalation decisions for monotherapy and combination therapy. The BLRM methodology will be implemented separately for Q1W dosing schedule and Q3W dosing schedule. At the time of each dose escalation decision, BLRM will be used to obtain, for each potential dose, an updated estimate of the toxicity curve and the posterior probabilities that the DLT rate for that dose lies in each of four toxicity intervals (underdosing, target toxicity range, excessive toxicity, and unacceptable toxicity). The four DLT toxicity intervals are defined as follows:

- [0%, 16%) Under-dosing range;
- [16%, 33%) Target toxicity range;
- [33%, 50%) Excessive toxicity range;
- [50%, 100%) Unacceptable toxicity range;

The dose with the highest posterior probability of lying in the Target Toxicity range will be the model-recommended dose for the next cohort. Additionally, the following constraints for the recommended dose will be maintained:

- The posterior probability of the DLT rate lying in the Excessive Toxicity or Unacceptable Toxicity range is less than 25%.
- The recommended dose is no more than two-fold (100%) of the previous dose.

Note that de-escalation as well as escalation is possible using this method.

Dose escalation will continue until:

i. An MTD is found:

At least 9 participants have been treated at the current target dose

AND

The posterior probability that the DLT rate for the current dose lies in either the excessive toxicity or unacceptable toxicity range is less than 25%

AND

The posterior probability that the DLT rate for the next higher dose lies in either the excessive toxicity or unacceptable toxicity range is greater than or equal to 25%.

OR

ii. The maximum administered dose has been reached and at least 9 participants have been dosed at that dose level.

OR

toxicity or      iii. All doses have a posterior probability of lying in either the excessive unacceptable toxicity range of greater than or equal to 25%

AND

At least two DLTs have been observed.

### 3.2. Japan: Dose Escalation (Monotherapy)

CCI

**Table 1 3+3 Dose-escalation Guidelines**

Number of Participants with DLT at a Given Dose Level	Action
0 of 3	Escalate to the next dose level
1 of 3	
Accrue 3 additional participants at current dose level for a total of 6 evaluable participants.
 
 
• If 0 of the additional 3 participants experience a DLT, escalate to next dose level.
 
• If <math>\geq 1</math> of the additional 3 participants experiences a DLT, stop dose escalation.
 

1 of 6	Escalate to the next dose level
$\geq 2$ of up to 6	Stop dose escalation

CCI dose escalation cohort will be analyzed separately from the monotherapy dose escalation study conducted outside CCI

The Japan monotherapy dose escalation cohort was closed to recruitment after 2 participants had been enrolled. Therefore, no decisions were made regarding dose escalation as 3 DLT evaluable participants were not recruited.

### 3.3. Final Analysis

The final analysis will be performed after the completion of the following sequential steps:

[figure not shown]
1. All participants have completed the study as defined in the protocol (see Protocol Section 4.3). Under Protocol Amendment 7, participants will be considered to have completed the study if they complete the safety follow-up until 90 days after last dose, start subsequent therapy or die. As per RAP version 4, the study will transition to a Post Analysis

Continuation of Treatment (PACT) phase, in which case the implementation of PACT will trigger the final analysis.

[figure not shown]
2. All required database cleaning activities have been completed and final database release (DBR) and database freeze (DBF) has been declared by Data Management (DM).

## 4. ANALYSIS SETS

CCI

CCI

#### **4.1. DLT Evaluable**

Additional considerations are needed for determining whether participants are DLT evaluable:

- Participants must receive at least 80% of the scheduled dose in the DLT period to be DLT evaluable. This only has implications on CCI
- 
- 
- 
- 
- 
- 
- 
- 
-

CCI

DLT reconciliation meeting(s) will be held to ensure all applicable participants in CCI [REDACTED] are correctly determined as DLT evaluable or not in the ADaM datasets and displays.

- Clinical, safety, statistics, clinical programming and clinical operations will attend as a minimum.
- S&P will create a listing of applicable participants with a derived DLT evaluable flag, which is calculated programmatically based on the criteria above.
- The clinical team will provide a listing of the same applicable participants with the DLT evaluable flag based on the DEMs and any other relevant information.
- Any differences between the clinical list and S&P list will be reviewed.
  - If possible, the S&P algorithm will be updated to match the listing provided by the clinical team.
  - If it is not possible to update the algorithm (for example, the necessary data has not been collected in the eCRFs), then the team will agree and approve the listing from clinical. The agreed listing from clinical will be deemed the final listing and will be used as the source data for the DLT evaluable flag (that is, for the analyses after the DLT reconciliation meeting(s), the DLT evaluable flag will come from the final list and will not be calculated programmatically by S&P).
- The meeting minutes will include the final DLT evaluable list. The meeting minutes will be filed in the eTMF.

## **5. PROTOCOL DEVIATIONS**

Important protocol deviations (including deviations related to study inclusion/exclusion criteria, conduct of the trial, participant management or participant assessment) will be summarized and listed based on the All Treated analysis set. The table and listing will include the crossover cohorts.

Protocol deviations will be tracked by the Study Team throughout the conduct of the study. These protocol deviations will be reviewed to identify those considered as important as follows:

- Data will be reviewed prior to freezing the database to ensure all important deviations are captured and categorized in the protocol deviations Study Data Tabulation Model (SDTM) dataset.
- This SDTM dataset will be the basis for the summary and listing of important protocol deviations.

The number and percentage of participants who entered the trial and had important protocol deviations defined as part of the protocol deviation management plan for the study will be summarized. The protocol deviations categories will be sorted in descending order based on total incidence, and within category, the protocol deviation coded terms will be sorted in descending order based on total incidence. A participant listing of the important protocol deviations will also be produced, including treatment, site ID, unique subject ID, subject ID, date of deviation, study day of deviation, period day of deviation, protocol deviation category, protocol deviation coded term, protocol deviation description and relationship to COVID-19. The listing will be sorted by treatment, site ID, unique subject ID, subject ID, and date of deviation.

A separate listing of all inclusion/exclusion criteria deviations will be provided based on the All Treated analysis set. This summary will be based on data as recorded on the inclusion/exclusion page of the eCRF. The listing will include site ID, treatment group, unique subject ID, subject ID, inclusion/exclusion type, protocol version and criteria description. The listing will be sorted by treatment, site ID, unique subject ID, and subject ID.

CCI

## 6. CONSIDERATIONS FOR DATA ANALYSES AND DATA HANDLING CONVENTIONS

[figure not shown]
### 6.1. Study Treatment & Sub-group Display Descriptors

All displays will be displayed by study part and order of treatment group as indicated below in the last column “Order in TLF”. The cohorts are ordered by increasing dose intensity considering the dose and regimen.

Treatment Group Descriptions				
REGIMENT Dataset		Data Displays for Reporting		
Code	Regimen Description	Study Part	Treatment Group Description	Order in TLF
CCI				

## Treatment Group Descriptions

CCI

### 6.1.1. Japan Monotherapy Cohort

Data from the Japan monotherapy cohort will be included as a separate cohort. The cohort will be displayed alongside the main study cohorts in Part 1A and will be included in the Part 1A Total column.

### 6.1.2. Imaging Substudy Combination Cohort

Data from the Imaging Substudy cohort will be included as separate cohorts. The cohorts will be displayed alongside the main study cohorts in Part 2A and will be included in the Part 2A Total column.

### 6.1.3. Crossover Cohorts

As per Protocol Amendment 6, participants in Part 1A may be considered on a case-by-case basis to transition to a cleared combination dose/frequency regimen as tested in Part 2A.

For participants who cross over to Part 2A from Part 1A, the data occurring prior to crossover will be considered for analysis in the Part 1A cohorts.

For all study population, safety and PK displays, the data occurring after crossover will be included in the applicable displays. In most cases, this will be via the addition of separate crossover combination cohorts (considered the standard approach in this study). When a different approach is required to display the crossover data, details are provided. The approach will be indicated in the programming notes column in Section 12.10 and in the mock shells. For the efficacy table, data occurring after crossover are not included in the display.

The crossover cohorts are labelled according to the subsequent combination therapy dose/regimen. All possible crossover cohorts have been listed in Section 6.1, however, only the crossover cohorts with at least one participant will be included in the displays.

Japan monotherapy participants who cross over to combination therapy will be included in the main study crossover cohorts (that is, there will not be separate Japan crossover cohorts).

The date of crossover is defined as in Section [12.6.4](#).

## **6.2. Baseline Definitions**

For all endpoints (except as noted in baseline definitions), the baseline value will be the latest pre-dose assessment with a non-missing value, including those from unscheduled visits. For crossover participants, the baseline value for data included in the crossover combination cohort will be the latest pre-combination dose with a non-missing value, including those from unscheduled visits. If time is not collected, Day 1 assessments are assumed to be taken prior to first dose and used as baseline.

For laboratory data, baseline will be the latest non-missing pre-dose value. If there are multiple assessments on the same day, the mean will be used as the baseline value.

Unless otherwise stated, if baseline data are missing, no derivation will be performed, and baseline will be set to missing.

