A listing of all laboratory data for participants with any value outside of normal range will be produced. The listing will include treatment group, site ID, unique subject ID, subject ID, age, sex, race detail, lab test with units, term, planned timepoint, date, study day, period day, value, normal range, change from baseline, normal range flag (Low/Normal Range/High), and grade. Crossover cohorts will be included in the listing.

A listing of urinalysis data for participants with any value of potential clinical importance will be generated. Crossover cohorts will be included in the listing.

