## 12.4. Appendix 4: Study Phase and Treatment Emergent Flag for Adverse Events

### 12.4.1. Study Phase

Assessments and events will be classified according to the time of occurrence relative to study intervention period.

**Pre-Intervention** is defined as time prior to the first dose of study intervention.

**On-Intervention** is defined as time from first dose to last dose plus 30 days. If time of assessment or study intervention is not collected, the following assessment on the first dose date will be assumed to be taken prior to the first dose and therefore considered pre-intervention: ECOG, ECG, lab, and vital signs, and first dose date is considered on-intervention for AE and concomitant medication.

**Post-Intervention** is defined as any time post on-intervention window, i.e. date > last dose date + 30 days.

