### 12.5.2. Reporting Standards

General	

 
• The current GSK Statistical Display Standards will be applied for reporting, unless otherwise stated (Library Location: https://myteams.gsk.com/:w:/r/sites/IDSLLibrary): 
 
• Section 4: Principles for All Displays
 
• Section 5: Principles for Data Listings
 
• Section 6: Principles for Summary Table
 
• Section 7: Principles for Graphics
 
 
 
	
GSK Statistical Display Principles will be followed in the creation of GSK standard and non-standard outputs	
Formats	

 
• GSK IDSL Statistical Principles for decimal places (DP's) will be adopted for reporting of data based on the raw data collected, unless otherwise stated.
 
• Numeric data will be reported at the precision collected on the eCRF.
 
• The reported precision from non eCRF sources will follow the IDSL statistical principles but may be adjusted to a clinically interpretable number of DP's.
 
• Summary Statistics: values will be reported relative to the precision on the eCRF. Min and max will be to the same as the raw data, mean and median to 1 extra decimal place, standard deviation to 2 extra decimal places.
 
• Listings: values will be displayed to the same precision on the eCRF
 
	

Planned and Actual Time	

 
• Reporting for tables, figures and formal statistical analyses: 
 
○ Planned time relative to dosing will be used in figures, summaries, statistical analyses and calculation of any derived parameters, unless otherwise stated.
 
○ The impact of any major deviation from the planned assessment times and/or scheduled visit days on the analyses and interpretation of the results will be assessed as appropriate.
 
 
 
• Reporting for listings: 
 
○ Planned and actual time relative to study drug dosing will be shown in listings.
 
○ Unscheduled or unplanned readings will be presented within the participant listings.
 
 
 
	
Unscheduled Visits	

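### First-dose-day labs, ECGs and vital signs without a collected time are all classed as pre-dose, even where the planned timepoint is post-dose

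*SAP*

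**What the plan says.** The general baseline rule in SAP Section 6.2 is that "the baseline value will be the latest pre-dose assessment with a non-missing value, including those from unscheduled visits". For records without a time it adds: "If time is not collected, Day 1 assessments are assumed to be taken prior to first dose and used as baseline". For laboratory data it further says: "If there are multiple assessments on the same day, the mean will be used as the baseline value".

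Section 12.4.1 applies the same idea to study phase. When the time of the assessment or of the study intervention is not collected, certain records on the first dose date are "assumed to be taken prior to the first dose and therefore considered pre-intervention: ECOG, ECG, lab, and vital signs". In the same sentence, "first dose date is considered on-intervention for AE and concomitant medication".

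Two other places bear on the point. Section 12.5.2 sets a default: "Planned time relative to dosing will be used in figures, summaries, statistical analyses and calculation of any derived parameters, unless otherwise stated". Section 8.3 lists the columns of the laboratory listing, among them "lab test with units, term, planned timepoint, date, study day, period day, value, normal range". So the laboratory data carry a planned timepoint, but the two rules above do not refer to it.

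**The concern.** Day 1 can hold both pre-dose and post-dose records. A rule that sorts them by date alone, when no clock time exists, puts a post-infusion value on the wrong side of the first dose. The record then does two wrong things: it contributes to the reference value, and it is withheld from the post-baseline data.

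The displays exposed are few but real. Listing 21 prints change from baseline. Section 8.4.1 flags QTcF changes of 31-60 and >60 msec. Table 3.18 is the only laboratory summary table in the display list, and its n is defined by post-baseline measurements. The plan already holds the information needed to avoid the error for scheduled records, and the rule does not use it.

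**Working it through.** The plan gives no figure to reproduce, so the check is a reading of the rules together, followed by an illustration with assumed values.

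**Rules side by side**

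- Sections 6.2 and 12.4.1 both make the assumption without exception. A post-dose planned timepoint does not switch it off, and neither does unscheduled status.
- Section 6.2 lets unscheduled records serve as baseline. For laboratory tests it averages values from the same day, so an untimed post-infusion value joins the mean.
- Section 12.5.2 would classify a scheduled post-dose record by its planned time, but only where nothing else is stated. Sections 6.2 and 12.4.1 can be read as stating something else, and no order of precedence is given.
- Section 12.5.2 also keeps unscheduled visits out of summaries, apart from worst-case post-baseline analysis and PK. An untimed unscheduled first-dose-day lab is already pre-intervention under Section 12.4.1, so it never reaches the worst-case analysis. No other rule in the SAP classifies it.
- For crossover participants, Section 6.2 moves the baseline to before the combination dose. The untimed rules speak of Day 1 and of the first dose date. They do not say whether the first combination dose day is covered.

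**Illustration (assumed ALT values, assumed ULN 40)**

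Pre-dose 30 and untimed post-infusion 150 on Day 1; later visit 60.

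- Baseline as written: (30 + 150)/2 = 90. Baseline from the pre-dose value alone: 30.
- Change at the later visit as written: 60 − 90 = −30. With the pre-dose baseline: 60 − 30 = +30.
- The Day 1 value is 150/40 = 3.75 × ULN and the later value is 60/40 = 1.5 × ULN. The 150 is the only value above 3 × ULN and is not post-baseline under the rule. The participant would be lost from any Table 3.18 row that depends on ALT >3 × ULN and that the 150 would otherwise satisfy.
- If the true pre-dose sample was taken on an earlier day, the 150 alone is the baseline, and the later change is 60 − 150 = −90 instead of +30.

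**Opposite direction (assumed values)**

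Pre-dose 60 and untimed post-infusion 30 on Day 1; later visit 90.

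- Baseline as written: (60 + 30)/2 = 45. Change: 90 − 45 = +45.
- With the pre-dose baseline: 90 − 60 = +30. Here the rule enlarges the later increase.

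If times are collected, none of this arises.

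**The case against.** The strongest reply is that the premise is not shown. The rules apply only where time is not collected. Section 12.7.2 separately defines missing data as requested data that were not supplied, and the programming note to Listing 9 uses the phrase not collected for items that the eCRF does not capture. A record whose time was requested but left blank may therefore fall outside the rule. The SAP does not say that laboratory times are uncollected or that post-dose Day 1 samples are scheduled; the schedule is in the protocol. This stands, and it is why the point is minor.

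A second reply is that the planned-time default in Section 12.5.2 already handles scheduled post-dose records. It offers a route, but one that gives way to specific rules, so it does not settle the matter.

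A reader might infer more than the text supports:

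- That every such error understates toxicity. It does not: the second illustration goes the other way.
- That acute CRS or infusion-reaction signals are lost. They are not: those events are reported as AEs in Tables 3.8 and 3.9, and for AEs the first dose date is on-intervention. DLT displays do not use the rule either.
- That any participant with such a record disappears from Table 3.18. Only one with no other exceedance would. A later ALT of 180 would be 180/40 = 4.5 × ULN and would be counted anyway.
- That abnormal results are hidden. Listing 21 still prints the raw value, planned timepoint, normal-range flag and grade.

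**Conclusion.** The point holds as a minor defect in a stated rule. As written, an untimed post-infusion record on the first dose day is pre-dose even when its planned timepoint says otherwise, and the plan does not say how an untimed unscheduled draw should be treated. The consequences are limited to change from baseline in Listing 21, QTcF change flags (viewed in RAPIDO DV, with no static display), and a possible lost participant in Table 3.18.

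This rests on three assumptions: that some first-dose-day records have no collected time, that some of those were taken after dosing, and that Table 3.18 counts abnormalities in post-baseline values, as its definition of n suggests. The number of records affected cannot be obtained from the SAP and is probably small. The sign of the distortion follows the acute change in the parameter.

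**What to change.** In Sections 6.2 and 12.4.1, limit the pre-dose assumption to untimed first-dose-day records whose planned timepoint is pre-dose, or which belong to the scheduled Day 1 visit and carry no post-dose timepoint. State that untimed records with a post-dose planned timepoint are post-dose. Say that the same rule applies on the first combination dose day for crossover participants.

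For untimed unscheduled first-dose-day records, do not average them into the baseline when a scheduled pre-dose value exists, and keep them in the worst-case post-baseline review.

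The cost is about two sentences and one programming condition, and the change can be made without sight of results. The downside is small: a few unscheduled draws that were truly taken before dosing would count as post-baseline. Classing every untimed unscheduled draw as post-dose for all purposes would be more debatable and is not needed.
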